6.2 Methods of minimizing bias

6.2.1 Randomization

Patients will be allocated 1:1 to either azithromycin for 5 days or matching placebo for 5 days through minimization, which allows balance between treatment groups for several characteristics at all stages of the trial [78].

The following characteristics will be considered:

- 1) **Age:** 3-9 years vs. 10-17 years [7].
- 2) **Patient care status:** ambulatory vs. hospitalized.
- 3) **Duration of respiratory tract symptoms and/or fever before presentation to the ED:**
≤6 days vs. >6 days [43, 79].
- 4) **Participating center:** 13 centers.

The allocation of a participant to the IMP based on the aforementioned characteristics will be done using the electronic data capture (EDC) system secuTrial®. The first participant will be truly randomly allocated by the system; for each subsequent participant, the treatment allocation that minimizes the imbalance on the selected characteristics between groups at that time will be identified by the system. This allocation will be made with a probability of 0.8 in favor of the intervention that would minimize imbalance between treatment groups. The random element (of 0.2) ensures that allocation is not fully deterministic.

The ZüriPharm AG at the University Hospital Zurich will assemble, blind, label, and distribute the IMP for each site to guarantee all safety regulations. Each kit (IMP, oral syringe, and measuring cup) has a unique medication ID. The medication ID and the associated treatment (active drug and placebo) are linked in a medication list, which is stored in secuTrial® by the study data manager at the CTC Zurich. The medication list in secuTrial® includes medication IDs for medication that is available at each center (e.g., ZH123, LU123) and guarantees enough supply for each treatment arm. The medication list is concealed to all other parties.

Prior to allocation, the local investigators (study physician or study nurse) must enroll the participants who fulfill all inclusion/exclusion criteria via the EDC and enter the respective characteristics. The EDC will then allocate the medication ID to the patient by minimization and release the medication ID to the investigator. Patients will be allocated to the IMP at the ED (for ambulatory patients) or as closely as possible to hospital admission (for hospitalized patients) within a maximum of 6h after ED admission.

Information about eligible patients that will undergo screening (section 7.2) will be collected in a screening log at the local sites by the treating physician or local investigators. Each eligible patient receives a patient ID (documented in the screening log). Patients who will be included and allocated to IMP (medication ID) will be documented in the designation log and entered into the electronic Case Report Form (eCRF) in secuTrial® by the local investigators. Patient ID, medication ID, and date of allocation will be added to the eCRF accessible from the local site. The designation log will be held at each site and in copy at the CTC Zurich.

6.2.2 Blinding procedures

Blinding will be ensured through the use of placebo, which is provided by the ZüriPharm AG and indistinguishable from the active treatment in any way but the active ingredient. ZüriPharm AG and the study data manager (who links medication ID to active drug and placebo in secuTrial®) are unblinded (section 6.2.1). All care-givers (including nurses, treating physicians), the parent (and patient), the investigators, and outcome assessors will be blinded to the allocated treatment. The trial statistician will be blinded when performing the blinded sample size review, but will be unblinded for the final analysis.

The medication ID released by secuTrial® will be entered into a screening log. This screening log will be stored locally in every study center and can be used as back-up for unblinding procedures in case the secuTrial® would not be available for any technical circumstances.

6.2.3 Other methods of minimizing bias

Not applicable.

6.3 Unblinding procedures (code break)

In the MYTHIC, no situations needing emergency unblinding are foreseen. AEs caused by drug toxicity and needing discontinuation of the drug are expected to be extremely rare when administering azithromycin in regular doses and for 5 days. The acute toxicity of a one-off azithromycin overdose is very limited. There is no specific antidote and management is symptomatic. Allergic reactions to any of the ingredients of the formulation can occur. However, these are extremely rare. In situations where an allergic reaction due to trial treatment is suspected, and further regimen doses are due, trial treatment is to be discontinued. The following criteria for discontinuation or modification (Table 6) guarantee safety in MYTHIC without the necessity of unblinding the IMP:

Table 6. Criteria and procedures for discontinuation or modification of the IMP.

Discontinuation criteria:	Modification criteria:

 Any change in the patient's condition that justifies the discontinuation of the IMP (e.g., need for ICU transfer). Unacceptable toxicity or AE (according to the prescribing information). Use of a medication with a known major drug interaction with azithromycin. Withdrawal of informed consent for IMP by patient/parent. 	
Ambulatory patients:
 
 Need for hospital admission. 
Hospitalized patients:
 
 Failure to maintain oxygen saturation $\geq 90\%$ with FIO_2 100%. Oxygen saturation $< 90\%$ for $> 48h$. Clinical features of severe respiratory distress/exhaustion and/or shock/sepsis.
Procedures:	Procedures:

 Stop IMP 	
 Treatment modification with antibiotics against atypical pathogens* and/or Switch to standard of care**

Important note: Decision about additional treatment with beta-lactams (such as amoxicillin) to avoid potential non-treatment of co-infecting bacterial pathogens (e.g., Streptococcus pneumoniae) in study patients will be made by the treating physician and will not be influenced by local investigators or TMT.*/**
	

* Treatment alternatives to the IMP (azithromycin as active drug) against atypical pathogens (e.g., *Mycoplasma pneumoniae*, *Chlamydia pneumoniae*) must be discussed between the local investigators and the TMT. These include clarithromycin (as another potent macrolide) or doxycycline in children ≥ 8 years of age (also as treatment option for infections with MRMP) [9]. In case of clinical suspicion of MRMP infection (e.g., worsening and/or non-responding symptoms), testing and (modifying) treatment for MRMP should be initiated irrespective of the study. The TMT will also support the local team at the participating centers in managing infections with (possible) MRMP.

** Decision about switch to standard of care (defined as treatment-as-usual, usual care, or routine care) will be made by the local team. The IMP should be continued for the total 5-day treatment duration whenever possible.

In case of need for emergency unblinding due to unforeseen circumstances in a study participant, the coordinating principal investigator or TMT must be contacted. They will be available around the clock by phone in case an emergency unblinding is deemed necessary. Unblinding of the respective study participant will occur through the secuTrial® database by a person with an appropriate right.

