Inclusion / exclusion criteria:	
Inclusion criteria:
 
Inclusion criteria for screening phase:
 
 • Children aged 3-17 years (from 3rd up to 18th birthday) presenting to the ED who will be managed ambulatory or will be admitted to general ward. • Clinical diagnosis of CAP: 
 1) Diagnosis defined as the treating physician's documented diagnosis of CAP; AND 2) Fever ≥38.0°C (measured by any method [i.e., ear, axillary, rectal, or forehead site] in the ED or via parent report observed in the last 24h); AND 3) Tachypnea (defined as RR above age-specific reference value) during the assessment in ED (triage or clinical examination). • Written screening consent for participation in screening phase signed by parents/legal guardians and the patient if ≥14 years of age. 
Additional inclusion criteria for intervention phase:
 
 • Positive Mp screening test result with the Mp IgM LFA (grade 2 or 3). • Written informed consent for participation in intervention phase signed by parents or legal guardians and the patient if ≥14 years of age. 
Exclusion criteria:
 
Exclusion criteria for screening phase:
 
 • None. 
Exclusion criteria for intervention phase:
 
 • Contraindication to azithromycin: Documented allergy to azithromycin; cardiovascular disease, including bradycardia, arrhythmias, and/or QT-interval prolongation*; myasthenia gravis. *Co-medication with arrhythmogenic or QT-interval-prolonging drug (www.qtdrugs.org) is no exclusion criteria but will be discussed with the local investigators and/or trial management team (TMT). • Underlying comorbidities: Cystic fibrosis or other chronic lung disorders (excluding asthma), primary or secondary immunodeficiency, sickle-cell anemia, or severe cerebral palsy. • History of recurrent pneumonia (two or more episodes) or severe pneumonia (ICU admission or complications of CAP such as lung abscess, effusion, and empyema) in lifetime. • Antibiotic treatment against Mp within the previous 7 days, including macrolides, tetracyclines, or fluoroquinolones. • Referral to ICU directly from the ED. • Inability to take oral medication.

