7. STUDY POPULATION AND INFORMED CONSENT PROCEDURE

7.1 Eligibility criteria

Inclusion criteria:

Inclusion criteria for screening phase:

- **Children aged 3-17 years** (from 3rd up to 18th birthday) presenting to the ED who will be managed ambulatory or will be admitted to general ward.
- **Clinical diagnosis of CAP:**
 - 1) **Diagnosis defined as the treating physician's documented diagnosis of CAP;** AND
 - 2) **Fever $\geq 38.0^{\circ}\text{C}$** (measured by any method [i.e., ear, axillary, rectal, or forehead site] in the ED or via parent report observed in the last 24h); AND
 - 3) **Tachypnea** (RR above the age-specific reference value as defined in section 5.1, Table 1 during the assessment in ED [triage or clinical examination]).

This trial aims to produce translational results generalizable to a “real-world” setting. In ED settings, the diagnosis of CAP is generally based on clinical criteria [8, 9]. Therefore, inclusion criteria for this study will not be based on radiological or laboratory diagnostics. However, according to our experience from previous studies and feedback from participating centers, we expect $\geq 90\%$ of children to have a CXR performed as part of their diagnostic routine.

- **Written screening consent for participation in screening phase** signed by parents or legal guardians and the patient if ≥ 14 years of age.

Additional inclusion criteria for intervention phase:

- **Positive *Mp* screening test result** with the *Mp* IgM LFA (grade 2 or 3) (section 6.1).
- **Written informed consent for participation in intervention phase** signed by parents or legal guardians and the patient if ≥ 14 years of age.

Exclusion criteria:

Exclusion criteria for screening phase:

- None.

Exclusion criteria for intervention phase:

- Contraindication to azithromycin: Documented allergy to azithromycin; cardiovascular disease, including bradycardia, arrhythmias, and/or QT-interval prolongation*; myasthenia gravis.
*Co-medication with arrhythmogenic or QT-interval-prolonging drug (<https://crediblemeds.org>) is no exclusion criteria but will be discussed with the local investigators and/or TMT.
- Underlying comorbidities: Cystic fibrosis or other chronic lung disorders (excluding asthma), primary or secondary immunodeficiency, sickle-cell anemia, or severe cerebral palsy.

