7.2 Recruitment, screening, and informed consent procedure

Patient information material about the MYTHIC Study will be provided to participating centers in form of a short one-page DIN A5 flyer with a QR code to the MYTHIC website that can be placed in the waiting areas of the ED. The MYTHIC website (www.mythic-study.ch) will be created with both public and member-only areas, including a short informational film. Any information material reviewed and endorsed by the relevant CEC will be also deposited in the publicly accessible area of the MYTHIC website.

The ED staff (triage nurse or treating physician) will inform the local investigators (study nurse, study physician, or GCP-trained ED consultant) about an eligible patient with diagnosis of CAP (pre-screening). The local investigators will check inclusion criteria for the **screening phase** and initiate contact. Eligible patients and/or their parent will receive a consent form for research projects with persons (HRO, chapter 2) providing sufficient information about the screening phase of the study to make an informed decision. The local investigators will obtain written screening consent, and perform the screening with the *Mp* IgM LFA from capillary blood and collect a NPS for *Mp* PCR. The *Mp* IgM LFA results will be available within 10min and will be communicated to the treating physician. In case of a positive *Mp* IgM LFA result, written informed consent for **intervention phase** participation will be obtained at the ED (for ambulatory patients) or as closely as possible to hospital admission (for hospitalized patients) within maximum 6h after the ED admission. This corresponds to randomization within 10h from presentation to the ED and will therefore provide time for parent (and patient) to read the consent.

All patients will be assessed against the inclusion and exclusion criteria as listed in section 7.1 for both the written screening consent (screening phase) and written informed consent (intervention phase), and will be considered eligible for enrollment into MYTHIC if they fulfill *all* the inclusion criteria and none of the exclusion criteria. There will be no exceptions to eligibility requirements at the time of randomization. Questions about eligibility criteria should be addressed prior to randomizing a participant. Eligibility will be reviewed and documented by a local investigator at each participating center before patients are randomized into the study.

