7.4 Criteria for withdrawal / discontinuation of participants

With consenting to the trial, the parent (and patient) is consenting, to trial treatment, trial FUP, and data collection. However, an individual patient may stop treatment early or be stopped early for any of the following reasons (section 6.3, Table 6, “**Discontinuation criteria**”):

- **Any change in the patient’s condition that justifies the discontinuation of the IMP (e.g., need for ICU transfer).**
- **Unacceptable toxicity or AE (according to the prescribing information).**

- **Use of a medication with a known major drug interaction with azithromycin.**
- **Withdrawal of consent for the trial by parent.**

As the patient's participation in the trial is entirely voluntary, the parent (and patient) may choose to discontinue the trial participation at any time without penalty or loss of benefits to which they are otherwise entitled. Although the parent (and patient) is not required to give a reason for discontinuing trial treatment, a reasonable effort should be made to establish this reason while fully respecting the patient's rights.

If at all possible, it should be established whether the withdrawal relates only to continued receipt of IMP or whether the family wishes to discontinue FUP. A parent who chooses to discontinue trial treatment should be encouraged to follow the trial procedures and FUP schedule. However, a decision to stop the patient's participation early must be accepted. In this case, the TMT should be informed of this in writing. Patients who discontinue IMP or stop trial FUP early will not be replaced in the trial (section 8.5).

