8.7 Concomitant interventions (treatments)

The diagnosis of CAP will be based on clinical criteria (section 7.1). Decisions about hospital admission or ICU transfer (during hospitalization) will be made by the local clinical team and will not be influenced by the study. All participating patients will receive standard of care supportive treatment for CAP according to international guidelines and local recommendations, including supplemental oxygen, intravenous treatment/fluids and/or nasogastric feeds/fluids, as clinically indicated.

Antibiotic treatment decisions will be made according to local, national, and international guidelines and based on the clinical assessment of the patient by the treating physicians. Current international guidelines recommend empirical amoxicillin treatment as first choice for antibiotic therapy in children with CAP [8, 9]. Decision about additional treatment with beta-lactams (such as amoxicillin) to avoid potential non-treatment of co-infecting bacterial pathogens (e.g., *Streptococcus pneumoniae*) in study patients will be made by the treating physician (section 6.3). Importantly, the lack of a bacterial cell wall makes *Mp* resistant to beta-lactams and those antibiotics do not exhibit anti-inflammatory effects.

All necessary concomitant medications are allowed and must be recorded. If a medication with a known major drug interaction with azithromycin is essential for a child's management and cannot be replaced by a drug that does not have an interaction with azithromycin, then the IMP should be stopped and the concomitant medication used (section 6.3, Table 6, “**Discontinuation criteria**”).

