9.3.3 Enrollment (day 1)

The *Mp* IgM LFA result will be available within 10min, and in case of a positive result, the following procedures will be performed:

Participation in intervention phase:

- Careful check for inclusion and exclusion criteria.
- Information on and obtaining of the **written informed consent**.
- Venous blood sampling for *Mp* IgM ASC ELISpot assay. Venous blood sampling is often routinely available because an IV line and/or venous blood sampling is performed for clinical reasons in many CAP patients presenting to the hospital. However, the venous blood sample is not required for study inclusion (to avoid exclusion because of refusal to draw blood for the study).

Clinical assessment:

- Medical history (e.g., duration of cough and/or fever before presentation to the ED).

Laboratory and radiological assessment:

- Capillary blood for biomarkers (could be taken together with the blood sample for the *Mp* IgM LFA).
- Venous blood sampling for *Mp* ELISA (if venous blood is available for the *Mp* IgM ASC ELISpot assay).
- CXR (no inclusion criteria but desirable to confirm the clinical diagnosis and often routinely performed in cases with CAP presenting to the hospital).

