9.3.4 Randomization (day 1)

- IMP dispensing.

Clinical assessment:

- Physical examination.
- VS (T, RR, HR, SpO₂) just prior to and/or the last time before randomization (or prior to the administration of antipyretic medication at the ED).
- Symptom review incl. AEs.
- Concomitant care review.

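### Section 7.1 does not exclude a child already on an essential, irreplaceable medicine with a major azithromycin interaction, although section 8.7 says the IMP should be stopped for that child

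*Protocol*

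**What the plan says.** **Entry.** The intervention-phase exclusions in section 7.1, repeated in the synopsis, define contraindication to azithromycin by three items: documented allergy, cardiovascular disease and myasthenia gravis. None concerns a current interacting medicine. The only text on co-medication risk is a footnote on arrhythmogenic or QT-prolonging drugs, whose use "is no exclusion criteria but will be discussed with the local investigators and/or TMT". The separate exclusion for antibiotics in the previous 7 days concerns prior treatment active against *Mp*, not interactions. Section 7.2 treats a child as eligible when every inclusion criterion and no exclusion criterion is met, and adds: "There will be no exceptions to eligibility requirements at the time of randomization".

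**Stopping.** Table 6 in section 6.3 lists, under discontinuation, "Use of a medication with a known major drug interaction with azithromycin", and the procedure is to stop the IMP. Section 7.4 repeats the entry. Section 8.7 covers a medicine with a known major interaction that is essential for the child. If it "cannot be replaced by a drug that does not have an interaction with azithromycin, then the IMP should be stopped".

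**Timing and consequence.** Section 8.2.1 places dose 1 directly after randomization. Section 11.4.1 requires at least 80% of the medication to have been used for the per protocol set (PPS), which section 11.4.2 makes the deciding set for non-inferiority. Section 7.4 adds: "Patients who discontinue IMP or stop trial FUP early will not be replaced in the trial".

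**The concern.** Entry and stopping rules should agree on any condition that can be known on day 1. Here they do not. A child who arrives already taking an essential, irreplaceable medicine with a major interaction passes section 7.1 and, at that same moment, meets the stop condition of section 8.7.

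At stake is a needless randomization. The family consents to a treatment that the protocol's own rules say to stop, and the child may receive an avoidable dose alongside an interacting medicine. The child is then very likely lost from the PPS, with no replacement. This does not depend on the statistical analysis plan, because eligibility and stopping rules belong to the protocol.

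**Working it through.** **1. The rules applied to one child.** Take a child already on an essential medicine with a known major azithromycin interaction and no substitute.

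| Step | Section | Result for this child |
|---|---|---|
| Exclusion criteria | 7.1, synopsis | No item applies, so the child is eligible |
| Eligibility check | 9.3.3: "Careful check for inclusion and exclusion criteria" | Nothing listed to act on |
| Review of other treatment | 9.3.4: "Concomitant care review" | May reveal the medicine, but no entry criterion is tied to it |
| Dose 1 | 8.2.1 | Given at once after randomization |
| Stop rule | 8.7, with Table 6 and 7.4 | Condition already met, so the IMP should be stopped |

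**2. Share of the course used at each stop.** The inputs are the mg per dose in Table 7. The share after *k* doses is (day-1 dose + (*k* − 1) × later dose) / course total.

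- Bands 0 and 2 to 5 (band 0 shown): 100/300 = 33.3%, 150/300 = 50.0%, 200/300 = 66.7%, 250/300 = 83.3% after 1, 2, 3 and 4 doses.
- Band 1: 150/470 = 31.9%, 230/470 = 48.9%, 310/470 = 66.0%, 390/470 = 83.0%.

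The 80% threshold is first met at dose 4. A stop at any earlier point takes the child out of the PPS.

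**3. Size against the planned allowance.** The plan's drop-out figure in section 11.2 reproduces: 0.10 + 0.05 × (1 − 0.10) = 0.145. Then 322 / (1 − 0.145) = 376.6, against the stated 376, which is a rounding difference of no importance here.

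- Expected PCR-positive patients: 376 × 0.90 = 338.4.
- Allowance for loss to follow-up or insufficient compliance: 338.4 × 0.05 = 16.9.
- Affected children, at an assumed rate of 0.1% to 1% (the protocol gives none): 376 × 0.001 = 0.4 to 376 × 0.01 = 3.8.

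Even the upper end lies well inside the existing allowance of about 17.

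**The case against.** The strongest reply is that a sensible investigator would not randomize this child, and that the protocol leaves room for that judgment. Much of this stands.

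- **Compulsion to randomize.** A reader might infer from section 7.2 that the site must randomize any child who meets the listed criteria. The text does not support this. It bars exceptions that would let in an ineligible child, and it asks for eligibility questions to be settled before randomization. A site may decline. What remains is that no criterion tells it to.
- **Automatic stopping.** Sections 7.4 and 8.3 are permissive: a patient may be stopped. Only section 8.7 says the IMP should be stopped, and only for an essential, irreplaceable medicine. The point is confined to that child.
- **Table 6 against section 8.7.** A reader might see a contradiction because Table 6 omits the condition in section 8.7. Section 8.7 cites Table 6, so the two can be read together. The gap lies between stopping and entry.
- **QT-prolonging drugs.** A reader might infer that the footnote admits children whom Table 6 would stop. That would require such drugs to count as a known major interaction, and the protocol does not say which drugs do. Case-by-case discussion is a deliberate choice and can stand.
- **Order of procedures.** A reader might infer that co-medication is reviewed only after randomization. Section 9.3.4 also lists vital signs taken before randomization, and section 9.3.3 already includes medical history. The order is too loose to carry that claim, and the medicine may well be noticed before dose 1.
- **Rarity.** Entrants are previously healthy and the main comorbidities are excluded, so the group is very small. Affected children also stay in the full analysis set, where non-inferiority is tested as well.

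None of this supplies the missing entry criterion.

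**Conclusion.** The point holds as a small gap in eligibility: section 7.1 and the synopsis do not exclude a child for whom section 8.7 already calls for stopping the IMP. Such a child can be randomized, given dose 1 and stopped, and is lost from the PPS without replacement if the stop comes before dose 4.

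Very few children are affected. The figure of 0 to 4 rests on an assumed rate of 0.1% to 1%, and the protocol names no specific medicine. A reader might infer a safety failure or a threat to the primary analysis. The protocol shows no harm from a single dose, and planned power does not change. This is a worthwhile tidy-up, suitable for the next amendment, and not a reason to hold the trial.

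**What to change.** 1. Add one intervention-phase exclusion to section 7.1 and the synopsis: *Current use of an essential medicine that has a known major interaction with azithromycin and cannot be replaced (see section 8.7).*
2. State in section 9.3.3 that current medication is checked as part of the Enrollment eligibility check, before randomization.
3. Keep the stop entry in Table 6 and section 7.4 as written, at most adding a cross-reference to section 8.7. Narrowing it to irreplaceable medicines would weaken a safety rule: a child actually taking a replaceable interacting drug, for example one prescribed elsewhere, would no longer meet it.
4. Leave the QT footnote as a case-by-case discussion, subject to the new exclusion.

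The cost is one line in two places and a clarification of a check that already takes place on day 1. There is no new procedure and no change to the sample size. The downside is that a very small number of otherwise eligible children are excluded.
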